5.5. Additional information recorded at the selection/inclusion visit

The following additional assessments will be recorded at the selection visit:

- Information on previous or concomitant psychological therapy (details on the type of therapy, number of hours per week), if any.
- Information on previous psychotropic treatment, if any.

5.6. Participant withdrawal

5.6.1. Withdrawal criteria

Premature discontinuation of IMP during the double blind treatment period (W000-W026) does not mean that the participant prematurely stops the participation in the study.

In the case of premature discontinuation of IMP during the double blind period and, if the patient does not require an important modification on his/her current background medical care, he/she will be invited to complete CARS2, SRS-2, CGI evaluations and AE assessment for W012 (if discontinuation occurs prior to W012) and W026 visit as planned in the investigation schedule (Section 4.2.2).

Important modification of current medical care is defined as follows:

- *Newly initiated formal behavioural, cognitive or cognitive-behavioural therapy*
- *Increase/decrease weekly prescribed hours >25% of behavioural, cognitive or cognitive-behavioural therapy*
- *Newly initiated or recently changed pharmacotherapy:*
 - o *Introduction of a psychotropic medication (considered as forbidden in the study, section 6.3)*
 - o *Introduction or dose increase of an antipsychotic*
 - o *Introduction or dose increase of ADHD treatment*

The following criteria will lead to a premature discontinuation of IMP:

- Serum potassium levels < 3mEq/L
- Any suicide attempt, whatever its severity
- High suicidal risk, according to investigator's judgment or with a suicidal ideation of 4 or 5 on C-SSRS-C
- Nephrocalcinosis observed at the renal ultrasound
- Occurrence of seizure(s)
 - o in a patient without any medical history of seizure.
 - o or in a patient with a medical history of seizure if this require any modification of the on-going anti-epileptic treatment.
- Any symptoms or signs of potential renal function failure.
- eGFR $\leq 80\text{mL}/\text{min}/1.73\text{m}^2$ (estimated glomerular filtration rate, Schwartz formula 2009).
- Clinically relevant nephropathy according to investigator's clinical judgment (based on broader sources including risk factors, medical history, clinical examination and biological parameters).
- Clinically relevant hypercalciuria.

In case of abnormal urinary calcium/creatinine ratio that may be the expression of a clinically relevant hypercalciuria, a retest should be performed as soon as possible. Based on these results, the investigator should have a discussion with the local paediatric nephrologist in order to assess whether it corresponds to the presence of a clinically

relevant hypercalciuria according to their clinical judgment (based on broader sources including risk factors, medical history, clinical examination and other biological parameters).

Additional urinary retest(s) and other appropriate exams should be performed if they judge them as relevant for the patient's safety.

- Absence of 2 consecutive planned electrolytes monitoring analysis.
- Absence of 2 consecutive planned urinary monitoring analysis.
- Occurrence of QT prolongation ($QTc_F \geq 480\text{ms}$), torsade de pointe and ventricular arrhythmia. Even if a 12-lead ECG reading and interpretation will be centralised, a local assessment of ECG exams is necessary for detection of medical urgencies and must be enclosed in the source data. Central reading reports for ECG overrule local reading for inclusion/exclusion/withdrawal criteria.
- Occurrence of a new psychiatric or other medical conditions leading to necessary administration of forbidden concomitant medication or likely to interfere with the conduct of the study.
- Any event or circumstances related or unrelated to the treatment justifying the discontinuation of treatment in the investigator's opinion (including treatment failure i.e. lack of efficacy).
- Major deviation to protocol if it interferes with the study evaluations and/or if it jeopardises participant's safety, e.g. any medical event requiring administration of an unauthorised concomitant treatment (see section 6.3).

Other criteria for premature discontinuation of IMP and for premature withdrawal from the study:

- Lost-to-follow up.
- Any non-medical circumstances leading to patient withdrawal (e.g. assent/consent withdrawal).

Information to be collected during the last visit of these participants is given in Section 5.6.2. These follow-up modalities are used to ensure the efficacy and safety evaluation of all participants who received the IMP.

Special conduct in case of gastrointestinal symptoms and weight loss

If the patient experiences digestive symptoms (≥ 3 liquid stools per day and/or ≥ 3 vomits per day) or digestive symptoms with a weight loss greater than 5%, the study treatment should be temporarily interrupted. Such an interruption will last 48h/72hours.

In such a case a monitoring of K^+ , Na^+ must be done locally prior to study treatment re-introduction. Further electrolytes follow up will be locally done according to the clinical opinion of the medical doctor.

If these symptoms are persistent following 72 hours, the study treatment should be definitely withdrawn.

5.6.2. Procedure

The investigator must notify the sponsor of study withdrawals by entering data of the withdrawal visit in the e-CRF. The investigator must record the reason and the exact date of the premature discontinuation from the study in the e-CRF. If more than one reason is given, the investigator must indicate the main reason.

In case of premature discontinuation from the study a withdrawal visit will be done as soon as possible after the last dose intake and within one week at the latest

In the case of premature withdrawal of IMP due to an adverse event (event requiring immediate notification or not), the investigator must make every effort to collect the information relating to the outcome of the event. If necessary, the information will be collected afterwards (see section 8.9). This information is recorded in that part of the e-CRF which concerns adverse events. If the investigator cannot collect the information from a visit, he/she must collect it from the doctor ensuring the follow-up of the participant.

If the study is stopped / treatment is discontinued as a result of an event requiring immediate notification, the procedure described in Section 8.9.2.5 is to be implemented.

The dispositions to be taken after the IMP discontinuation are described in Section 6.5.

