8.2. Methods and measurement times

The **Columbia Suicide Severity rating Scale Children's version (C-SSRS-C)** ([Posner, 2007](#)) ([Posner, 2011](#)) assesses suicidal ideation and suicidal behaviour. Investigator will complete an e-training on this tool prior to the study start.

The C-SSRS-C includes two forms:

- Baseline/Screening version: completed at W000

- Since Last Visit version: to be completed at W012, W026, W038, W052 or at the withdrawal visit in case of premature withdrawal

The **Paediatric Adverse Event Rating Scale (PAERS)** (Shapiro, 2009) is an inventory report designed to identify signs/symptoms experienced by the patient since the study treatment initiation. Investigator will complete an e-training on this tool prior to the study start.

The PAERS will be completed:

- o During the Double Blind period at: W000, W000+Day 17, W004, W008, W012, W016, W020, W026 visits
- o During the Open Label period at: W026+Day17, W030, W034, W038, W042, W046, W052 visits
- o At the withdrawal visit in case of premature withdrawal

PAERS includes three forms:

- Youth form, to be completed when possible by the patient,
- Parent form, to be completed by a parent/legal representative or caregiver (when applicable).
 - o As far as possible same person should complete the form during the study
- Clinician form filled after assessment of youth form and parent forms

Physical examinations

- DBP, SBP and heart rate must be always assessed. Appropriate conditions are assessment in a sitting or lying position after 5-minute rest and at 1mn after standing position (orthostatic hypotension: known effect of bumetanide):
 - o At Selection
 - o During the Double Blind period at: W000, W002, W012, W026 visits
 - o During the Open Label period at: W028, W038, W052 visits
 - o At the withdrawal visit in case of premature discontinuation.DBP and SBP will be measured with the specific device provided by the Sponsor for the study.
- Body weight must be assessed:
 - o At Selection
 - o During the Double Blind period at: W000, W000+Day17, W004, W008, W012, W016, W020, W026 visits
 - o During the Open Label period at: W026+Day17, W030, W034, W038, W042, W046, W052 visits
 - o At the withdrawal visit in case of premature withdrawal.
- Height must be assessed:
 - o At Selection
 - o During the Double Blind period at: W012, W026 visits
 - o During the Open Label period at: W038, W052 visits
 - o At the withdrawal visit in case of premature withdrawal

12-lead ECG

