3.6. Safety analysis

All safety analyses will be performed on the taken treatment at W000 as following:

- For the double-blind period in the SS by treatment group (S95008 vs placebo).
- For the open-label period: in the SSO on the Placebo/S95008 arm.
- For the combined period: in the SSC on the S95008/S95008 arm.

Six periods are of interest to present accurately the safety endpoints. The start and end date of these periods are summarized in the following table:

Table (3.6) 1 - Definition of periods of emergence for safety events

| Period ID | ANALYSIS PERIOD | START | END |
|------------------|--|--|--|
| #1 | Emergent during the double-blind period | First intake in double-blind | End of double-blind period (including W26) |
| #2 | Treatment Emergent during the double-blind period | First intake in double-blind | Min(Last intake in double-blind + 2 days, First intake in open-label) |
| #3 | Emergent during the open-label period | First intake in open-label (W26 not included) | End of open-label period (including W52 and follow-up) |
| #4 | Treatment Emergent during the open-label period | First intake in open-label (W26 not included) | Last intake in open-label + 2 days (included) |
| #5 | Emergent from the combined period | First intake in double-blind | End of open-label period (including W52 and follow-up) |
| #6 | Treatment Emergent from the combined period | First intake in double-blind | Last intake in open-label + 2 days (included) |

Listing of main safety data (including adverse events) and start/end date of each period will be provided for:

- Patients who had a delay superior to 30 days between the double-blind and the open-label period will be listed separately.

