3.6.2. Columbia Suicide Severity Rating Scale Children's version

Definition:

The C-SSRS-C data will be mapped to Columbia Classification Algorithm for Suicide Assessment (C-CASA) (Guidance for Industry, Suicidality, FDA CDER, September 2010) following C-SSRS Scoring and Data Analysis Guide (February 2013) ([C-SSRS Guide](#)). The following endpoints will be thus considered:

11 preferred C-SSRS categories:

- For Suicidal ideation:
 - Wish to be dead (category 1).
 - Non-specific active suicidal thoughts (category 2).
 - Active suicidal ideation with any methods (not plan) without intent to act (category 3).

- Active suicidal ideation with some intent to act, without specific plan (category 4).
- Active suicidal ideation with specific plan and intent (category 5).
- For Suicidal behaviour:
 - Preparatory acts of behaviour (category 6).
 - Aborted attempt (category 7).
 - Interrupted attempt (category 8).
 - Actual attempt (non-fatal) (category 9).
 - Completed suicide (category 10).
- Self-injurious behaviour without suicidal intent (category 11).

Endpoints derived from these C-SSRS categories:

- Suicidal ideation or behaviour: at least one “yes” answer present at any assessable visit (*i.e. categories 1 to 10 analysable*) during the considered period to any one of the 1 to 10 categories.
- Suicidal ideation: at least one “yes” answer present at any assessable visit during the considered period to any one of the 1 to 5 categories.
- Suicidal behaviour: at least one “yes” answer present at any assessable visit during the considered period to any one of the 6 to 10 categories.
- Suicidal ideation score: maximum suicidal ideation category (1-5 on the CSSRS) among any assessable visit of the considered period; 0 if no ideation is present.

Baseline:

For suicidal ideation and suicidal behaviour (for items and the four associated derived C-SSRS endpoints), baseline will be defined as the value at W000, lifetime.

Analyses:

The 11 preferred C-SSRS categories as well as the four associated derived C-SSRS endpoints will be described during the double-blind (resp. open-label, combined) treatment period (*i.e. periods #2, #4 and #6*). Moreover, a listing of all patients having at least one post-baseline category equal to “yes” will be performed.

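### A protocol-compliant withdrawal visit on days 3 to 7 after the last dose puts its look-back C-SSRS-C form outside the SAP's by-arm suicidality tables, which stop at day 2

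*Protocol*

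**What the plan says.** **Timing of the withdrawal visit.** For children who leave the study early, protocol 5.6.2 sets this rule: "a withdrawal visit will be done as soon as possible after the last dose intake and within one week at the latest". Protocol 4.2.2 also requires the withdrawal visit when only IMP is stopped during the double-blind period, and sets no separate time limit for that case.

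**The form used.** Protocol 8.2 lists the "Since Last Visit version: to be completed at W012, W026, W038, W052 or at the withdrawal visit in case of premature withdrawal". The investigation schedule in 4.2.2 places the C-SSRS-C at W000, W012 and W026 in the double-blind period and at the withdrawal visit. The off-drug W012 and W026 visits for children who stop IMP but stay in the study do not include it.

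**The analysis window.** SAP 3.6.2 says that the 11 categories "as well as the four associated derived C-SSRS endpoints will be described during the double-blind (resp. open-label, combined) treatment period", and identifies these as periods #2, #4 and #6. Table (3.6) 1 of the SAP ends period #2 at "Min(Last intake in double-blind + 2 days, First intake in open-label)" and periods #4 and #6 at "Last intake in open-label + 2 days (included)".

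**What places an answer in a period.** For suicidal ideation, SAP 3.6.2 needs a positive "answer present at any assessable visit during the considered period to any one of the 1 to 5 categories". The other three derived endpoints are likewise defined over assessable visits of the period. SAP 3.6 presents the double-blind period by treatment group in the Safety Set.

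**Link to stopping.** Protocol 5.6.1 lists any suicide attempt among the criteria for discontinuing IMP, and also: "High suicidal risk, according to investigator's judgment or with a suicidal ideation of 4 or 5 on C-SSRS-C".

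**The concern.** A 2-day tail suits a measurement that describes the day it was taken. A blood sample drawn on day 5 off drug says little about the last day on drug. A Since-Last-Visit questionnaire is different: completed on day 5, it covers the whole interval back to the preceding form, and nearly all of that interval was on treatment. If the visit date alone decides, those on-treatment answers leave the by-arm C-SSRS tables.

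The loss falls only on children who stop early. Completers take their last dose on the morning of the scheduled visit (protocol 6.1), so their forms are always inside the window. Suicidality is a declared safety endpoint and also a reason for stopping. An event between scheduled visits that leads to stopping would next be recorded on the withdrawal form. If stopping differs between arms, so does the loss.

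**Working it through.** **1. Day count.** Let day 0 be the day of the last intake.

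- Visit days allowed by protocol 5.6.2: 0, 1, 2, 3, 4, 5, 6, 7, which is 8 days.
- Days inside period #2, #4 or #6: 0, 1, 2, which is 3 days.
- Days allowed but outside: 3 to 7, which is 5 days. 5/8 = 62.5% of the allowed days.

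**2. Is there another form to fall back on?** In the double-blind period the post-baseline forms are W012, W026 and the withdrawal visit.

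| Child | Post-baseline C-SSRS-C in the period #2 tables |
|---|---|
| Completes the double-blind period | W012 and W026 |
| Stops after W012, withdrawal visit on days 0 to 2 | W012 and withdrawal form |
| Stops after W012, withdrawal visit on days 3 to 7 | W012 only |
| Stops before W012, withdrawal visit on days 0 to 2 | Withdrawal form |
| Stops before W012, withdrawal visit on days 3 to 7 | None |

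**3. How many children could be affected?** The only input is the planning figure in protocol 10.1 and SAP 1.3. It reproduces:

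- Per arm, for effect size 0.5, 90% power and two-sided 5%: 2 × (1.960 + 1.282)² / 0.5² = 84.1, rounded up to 85, so 170 in total. Exact t-test power at 85 per arm is 0.900.
- Allowing for 15% withdrawal: 170 / (1 − 0.15) = 200.
- Expected withdrawals: 0.15 × 200 = 30.

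The documents do not give the share of withdrawal visits held after day 2, so it is an assumption:

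| Assumed share after day 2 | Forms outside the window (30 × share) |
|---|---|
| 10% | 3 |
| 25% | 7.5 |
| 50% | 15 |
| 62.5% (even spread over days 0 to 7) | 18.75 |

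These are counts of forms, not of positive answers. They are upper figures for each share, because they give all 30 children a withdrawal visit.

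**4. After the change.** If the form is assigned to the period it looks back on, for visits up to day 7, then 0 of the 8 allowed days are lost instead of 5.

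**The case against.** **The exclusion is inferred.** For laboratory, vital-sign and ECG data (SAP 3.6.3, 3.6.4.1, 3.6.4.2) the SAP says in terms that a date inside the period decides. Section 3.6.2 has no such sentence. This is true, and it leaves some room for interpretation. But all four derived endpoints are defined over visits of the considered period, and nothing assigns a later form back to treatment. A programmer following the text would leave it out.

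**A reader might infer that children stopped for ideation of 4 or 5 are the ones whose answer is lost.** The documents do not support that in general. The criterion can be met on a scheduled form completed while the child is on IMP. That answer is inside the window, and since the endpoints take any positive answer or the maximum category, a later withdrawal form cannot remove it. Only answers first recorded on a late withdrawal form are exposed.

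**A reader might infer that on-treatment suicidality disappears from the report.** It does not. Protocol 8.3 treats relevant events found through a safety scale as adverse events. SAP 3.6.1 tabulates treatment-emergent events by when they occur, and serious emergent events over period #1, which runs to the end of the double-blind period. SAP 3.6.2 also lists every child with a positive post-baseline category, with no period limit. What remains is that a listing gives no rate by arm, and the suicidal ideation score has no adverse-event equivalent.

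**The size is assumed.** Protocol 5.6.2 asks for the visit as soon as possible, so early visits should dominate and the even-spread figure of about 19 is high. Children lost to follow-up or whose consent is withdrawn may have no withdrawal visit at all. Both points stand.

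**It is a minor descriptive table.** The children are under 7, those at high or current suicide risk are excluded (criteria 18 and 38), and no efficacy conclusion depends on it. This limits the priority, but the correction is cheap.

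**Conclusion.** The point holds in a limited form. The protocol's one-week allowance and the SAP's 2-day window do not fit together for a look-back questionnaire. As written, a compliant withdrawal form on days 3 to 7 is outside the by-arm C-SSRS tables, and a child who stopped before W012 and was seen that late has no post-baseline result in them.

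The size is about 3 to 19 forms out of roughly 30 withdrawals, on three assumptions: 15% withdrawal as planned, 10% to 62.5% of withdrawal visits after day 2, and a withdrawal visit for every child who stops. The number is smaller if some have none. Few positive answers are expected at this age, although with rare events one or two omissions can change a descriptive comparison. The conclusion also rests on reading SAP 3.6.2 as placing an answer by its visit, which is what its endpoint definitions say.

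The between-arm comparison is affected only through period #2. Periods #4 and #6 have the same cut-off, but SAP 3.6 presents each for a single arm.

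**What to change.** Add to SAP 3.6.2:

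- A Since-Last-Visit C-SSRS-C form from a withdrawal visit counts in the treatment period that its look-back covers (#2, #4 or #6) when two conditions hold: the preceding C-SSRS-C form is dated on or before the last intake, and the withdrawal visit is within the protocol's one week of the last intake.
- Forms dated more than 2 days after the last intake are flagged in the listing.
- Withdrawal forms later than one week are shown separately. This bound is needed because the protocol sets no deadline for the withdrawal visit when only IMP is stopped; without it, weeks off drug could be counted as treatment.
- The 2-day limit stays for laboratory values, vital signs and ECG.

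The cost is a short SAP addition and one programming rule, with no new data or visits. The downside is that a positive answer arising in the few off-drug days before the visit may be counted as on treatment; the flag makes these cases visible.

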5.6.3. Lost to follow-up

When the investigator has no news of the participant, he/she must make every effort to contact him/her and his/her parents/legal representative(s) and caregiver (when applicable) or a person around them (phone calls, letters including registered ones... etc.), to establish the reason for the discontinuation of IMP and to suggest the participant comes to an end-of-study visit. If all these attempts to contact the participant fail, the investigator can then declare the participant "lost to follow-up". The investigator should document all these attempts in the corresponding medical file.

6. TREATMENT OF PARTICIPANTS

6.1. IMP administered

During the run in and the follow up periods patients will not receive IMP.

During the treatment period (from W000 to W052), the patient will take orally twice a day:

- **in the morning at wake-up**

- **in the afternoon, 3 hours before going to bed at night at the latest**

the following volume of the oral solution:

For patients with a weight < 25kg:

- The volume (mL) = 0.04 x body weight (kg) twice per day from inclusion to W052

For patients with a weight ≥ 25kg:

- 1 ml twice per day from inclusion to W052

The study treatment should be taken at least 15 minutes before any food intake.

The first study treatment intake will take place in the afternoon at the latest 3 hours before going to bed at night of the inclusion visit day.

The last IMP intake will take place in the morning of the day of the scheduled visit.

The description of the IMP is detailed in Section 4.4.1.

6.2. IMPs dispensing

Double blind treatment period: IMP box dispensing will occur at W000 (1 Kit A), W004 (1 Kit A), W008 (1 Kit A), W012 (1 Kit A), W016 (1 Kit A), W020 (1 Kit A). The kit number of Kit A will start by 20XXXX and the label will be orange.

Open label safety extension period: IMP box dispensing will occur at **W026 (1 Kit B)**, W030 (1 Kit B), W034 (1 Kit B), W038 (1 Kit B), W042 (1 Kit B), W046 (1 Kit B). The kit number of Kit B will start by 22XXXX and the label will be blue.

The Kit number(s) will be given to patient according to number(s) allocated by IRS (please see details in IRS manual).

The detachable portion of the label on the IMP box must be stuck by the investigator on an IMP label collection form or on the prescription form where the IMPs are dispensed by a pharmacist.

